# On patient level
tbl summary(
      data = dataEndpoints, by = group, missing = "no",
      include = c(sae pat, n sae, ...),
      label = list(sae pat ~ "Number of Patients with a SAE",
                   n sae ~ "Number of SAE", ...),
      type = all continuous() ~ "continuous2",
      statistic = list(all continuous()~ c("{N nonmiss}", "{mean}\u00B1{sd}",
                        "\{median\} (\{p25\}-\{p75\})"),
                        all categorical() ~ \{n\}/\{N \text{ nonmiss}\} (\{p\}\%\})))%>%
      add p(pvalue fun = label style pvalue(digits = 3),
            test = list(
                  all categorical()~ "chisq.test",
                  all continuous()~ "t.test"))
# On the events in each group
tbl summary(
      data = dataSAEs, by = group, missing = "no",
      include = c(sae outcome, sae serious, ...),
      label = list(sae outcome ~ "Outcome of SAE",
                   sae_serious ~ "Seriousness of SAE", ...),
      type = all_continuous() ~ "continuous2",
      statistic = list(all continuous()~c("{N nonmiss}", "{mean}\u00B1{sd}",
                        "{median} ({p25}-{p75})"),
                        all categorical() ~ ^{n}/{N \text{ nonmiss}} ({p}%)"))
# Kaplan-Meier curves with log-rank tests
SurvObj <- Surv(event time, event_status,</pre>
                                                   data
                                                          =
                                                                dataEndpoints)
km.by.treat <- survfit(SurvObj ~ group, data = dataEndpoints,</pre>
                        conf.type = "log-log")
plot(km.by.treat)
dataEndpoints %>%
  gtsummary::tbl survfit(y = Surv(time, status),
                          label header = "**{time} weeks**",
                          include = "group", times = 364/7) %>%
  gtsummary::add p()
# Cumulative incidence functions with Gray's test
cuminc(Surv(event time, event status) ~ group, data = dataEndpoints) %>%
  ggcuminc() +
  ylim(c(0, 1)) + labs(x = "Days") +
  add confidence interval() +
  add risktable()
cuminc(Surv(event_time, event_status) ~ group, data = dataEndpoints) %>%
  tbl_cuminc(times = 364/7, label_header = "**{times} weeks cuminc**") %>%
  tidycmprsk::add_p()
# Negative binomial Regression for recurrent events
mod.les <- glm.nb(event rate ~ intervention + center +</pre>
                   offset(log(FUtime)), data = secEndpoints)
tmt.means <- emmeans(mod.les, ~ intervention, type = "response",</pre>
```

Confidential Page 18 of 21

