### 2.3 Sample Size

For sample size calculation we assume a common standard deviation of 16 points in the total MDS-UPDRS (parts I, II and III) and an overall type 1 error rate of 5%. Such a standard deviation was seen in Holden et al (2018). This estimate is further supported by a blinded sample size review performed on a blinded data export from August 23, 2024. A sample size of 162 participants per group gives an 80% power given a difference of 5 points in the total MDS-UPDRS at 52 weeks between the NR and the placebo group (324 in total). A difference of this magnitude was reported to be within the clinically meaningful range (see Wyman-Chick et al (2018)). Accounting for approx. 20% drop out, 200 participants per group (400 in total) are required.

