#### 5.2 Analysis methods

#### Primary endpoint analysis

The primary endpoint, the MDS-UPDRS changes from baseline to week 52 between the NR and placebo group, will be analyzed using Gaussian linear models for repeated measures (MMRM) with intervention, center, time (week 13, 26, 39, and 52), and intervention-by-time interaction as factors, and baseline MDS-UPDRS score as covariate. Centers with fewer than 20 patients are pooled into one center. The error terms are assumed to follow a multivariate normal distribution with unstructured covariance. Least square mean changes for both groups as well as the difference between the least squares treatment group means will be reported with 95% CIs and p-value testing the null hypothesis of no treatment effect.

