#### Secondary endpoints analyses

The analyses of continuous secondary endpoints with multiple measurement times, namely the MDS-UPDRS part I, II and III and the NMSS total and domain scores, are compared between the

Confidential Page 15 of 21

treatment groups by the MMRM model as described for the primary endpoint. The change in the mean Striatal Binding Ratio (SBR), in the total MOCA score and in the EQ-5D-5L index value are compared between the treatment groups by analysis of covariance (ANCOVA) with intervention and center as factors and baseline value as covariate. Least square mean changes for both groups as well as the difference between the least squares treatment group means will be reported with 95% CIs and p-value testing the null hypothesis of no treatment effect. The family-wise error rate across the key secondary endpoints, namely MDS-UPDRS part 1, 2 and 3, mean striatal binding ratio and NMSS total score, will be controlled by application of the Hochberg procedure. The key secondary endpoints are only tested for significance if the primary endpoint is statistically significant. The analyses of other secondary endpoints and safety parameters will have an exploratory character and will therefore not be adjusted for multiple testing.

The Hoehn and Yahr stage at 52 weeks will be compared between the treatment groups by ordinal regression with intervention, center and baseline stage as factors.

```
library(ordinal)
library(emmeans)
library(rstatix)
mod.sec <- clm(HoehnYahr w52 ~ HoehnYahr.BL + group + center,</pre>
                  link = 'logit', data = dataEndpoints)
emm.ord <- emmeans(mod.sec, ~ HoehnYahr w52 | group, mode = 'prob',
                   adjust = 'none') %>% as.data.frame()%>%
mutate(Prob = sprintf('%.3f (%.3f, %.3f)', prob, asymp.LCL, asymp.UCL)) %>%
dplyr::select(HoehnYahr.V10, RANDTRT, Prob) %>%
pivot wider(values from = Prob, names from = group)
comp <- pairs(emmeans(mod.sec, specs = 'group'))</pre>

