#### 5.5 Harms

Safety endpoints will be analyzed descriptively by treatment group using standard statistic measures depending on the data type (e.g. frequencies and percentages for categorical variables and mean, standard deviation, median and IQR for continuous variables). For events of particular interest (e.g. neoplastic disease and cardiovascular events) Kaplan-Meier curves or cumulative incidence functions in case of competing events stratified by treatment group will be computed and compared by log-rank tests resp. Gray's test. For recurrent events and to account for variable

Confidential Page 17 of 21

follow-up times, event rates will be reported with rate ratios comparing NR with placebo and 95% CI. We will use Poisson regression with adjustment for over dispersion or negative binomial regression models with offset for follow-up time and possibly a mixture component to account for zero-inflation.

```
library(gtsummary)
library(survival)
library(ggsurvfit)
library(tidycmprsk)
library (MASS)

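### The visible recurrent-event code averages log rates over fixed centre effects, so for sparse event types one centre without events can push both arms' reported rates far below events per person-time

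*SAP*

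**What the plan says.** Section 5.5 states that, for recurrent events and variable follow-up, "event rates will be reported with rate ratios comparing NR with placebo and 95% CI". It names overdispersed Poisson or negative binomial models with a follow-up offset, and "possibly a mixture component to account for zero-inflation". The prose does not mention centre.

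The code at the end of section 5.5 is more specific. The model line begins "mod.les <- glm.nb(event rate ~ intervention + center" and continues "offset(log(FUtime)), data = secEndpoints". Arm means are then requested with "tmt.means <- emmeans(mod.les, ~ intervention, type = 'response", where the text breaks off after a comma. No argument on weights, on the scale of averaging or on the offset can be seen.

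Two other places bear on this. Under the primary endpoint, section 5.2 says "Centers with fewer than 20 patients are pooled into one center". That rule goes by number of patients, not of events, and is not stated to apply to the harms models. Section 5.2 also says: "The analyses of other secondary endpoints and safety parameters will have an exploratory character".

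**The concern.** In a log-link model with centre as a factor, the maximum-likelihood coefficient of a centre with no events is minus infinity. The software stops at some large negative number that depends on its convergence rule. Averaging the linear predictor over centres carries a share of that number into the mean of each arm, and exponentiating afterwards turns it into a multiplicative loss. The loss is the same in both arms, so the contrast gives no warning.

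At stake are the absolute rates, which readers use to judge how often a harm occurs. Empty centres are most likely for uncommon event types.

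**Working it through.** **Inputs from the SAP.** Total sample size (section 2.3: "200 participants per group (400 in total) are required"), 1:1 allocation, and the model and call quoted above. The SAP gives no event rate and no number of centres, so it has no figure of its own to reproduce. These are assumptions: number and size of centres, true event rate, follow-up of 0.7 to 1 year, and negative binomial dispersion 0.5. Event counts were used as the response.

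**Step 1: size of the loss.** With K centres weighted equally and one empty centre whose coefficient stops at b, the arm mean is multiplied by about exp(b/K). With m empty centres it is about exp(m·b/K).

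- K = 9, b = −16: exp(−16/9) = 0.17. With b = −18: exp(−18/9) = 0.14.
- K = 9, two empty centres, b = −16: exp(−32/9) = 0.03.

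**Step 2: running the model and call in R.** One simulated data set per row, equal centres, one centre set to zero events. Rates are per year (offset set to zero), placebo/NR.

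| Centres | True rate | b | Events/person-time | Model-based rate | Placebo ratio | exp(b/K) |
|---|---|---|---|---|---|---|
| 4 | 0.15 | −18.3 | 0.106/0.088 | 0.0015/0.0012 | 0.014 | 0.010 |
| 4 | 0.50 | −22.5 | 0.359/0.360 | 0.0017/0.0017 | 0.005 | 0.004 |
| 8 | 0.15 | −18.6 | 0.159/0.095 | 0.0164/0.0098 | 0.10 | 0.10 |
| 10 | 0.15 | −34.7 | 0.106/0.165 | 0.0032/0.0050 | 0.030 | 0.031 |
| 12 | 0.15 | −17.1 | 0.157/0.114 | 0.0365/0.0267 | 0.23 | 0.24 |
| 12 | 0.50 | −24.3 | 0.482/0.437 | 0.0654/0.0597 | 0.14 | 0.13 |

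The fall runs from about 4-fold (0.157/0.0365 = 4.3) to about 200-fold (0.359/0.0017 = 211). The 95% CIs ran from practically zero to an astronomically large number or infinity.

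**Step 3: repeated simulation, 9 centres of 25 to 90 patients, 400 in total.** The reported rate was about 0.17 to 0.18 of crude with one empty centre and 0.03 with two, as in step 1.

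**Step 4: how likely an empty centre is.** With dispersion 0.5 and one year of follow-up, a centre of n patients has no events with probability (1 + 0.5λ)^(−2n).

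- n = 20: λ = 0.05 gives 1.025^(−40) = 37%; λ = 0.15 gives 5.5%; λ = 0.5 gives 0.01%.
- n = 50: λ = 0.05 gives 8.5%; λ = 0.15 gives 0.07%.

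In the 9-centre setting, two simulations put the chance of at least one empty centre at 32% and 40% for 0.10 events per patient-year, at 82% and 86% for 0.05, and at 99% in both for 0.03.

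**Step 5: what cures it.** In step 2 the centres were equal, so proportional and equal weights almost coincide and cannot be told apart. With unequal centres, proportional weights alone still gave about 0.24 to 0.29 of the crude rate. Averaging on the response scale gave, for the 10-centre row, 0.091/0.141 at the mean follow-up of 0.85 year. That is 0.091/0.85 = 0.107 and 0.141/0.85 = 0.166 per year, against crude 0.106/0.165.

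**Step 6: the rate ratio.** It equals the ratio with the empty centre dropped: 1.550 and 1.550 with 10 centres, 0.827 and 0.827 with 4 centres at 0.15.

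**The case against.** The strongest objection is that the call is incomplete. The lost arguments may ask for response-scale averaging, and text lost in reading is no fault of the plan. This stands as a condition on the point. It does not remove it, because nothing visible in the code or prose sets the averaging on that scale.

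Second, the snippet looks like a template. The prose of section 5.5 does not tie the arm rates to this call, and the response is labelled a rate although an offset is also fitted, so the lines need rewriting anyway. That is a reason to make both corrections together.

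Third, the scope is narrow. Section 5.5 sends events of particular interest to Kaplan-Meier or cumulative incidence curves, and for common events an empty centre is very unlikely. Sparse types of serious event could still reach the rate model. An absurd confidence interval, with patient and event counts by arm tabulated alongside, would probably be noticed. This stands and limits the severity, but specified code should not depend on it.

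A reader might infer three stronger things that the SAP does not support:

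- That the treatment comparison is biased. It is not (step 6).
- That equal weighting of centres is the cause, so that other weights would repair it. The cause is averaging on the log scale (step 5).
- That the rates are wrong even without an empty centre. In the R runs without one, the model-based rates were about 2% to 13% below crude (4 centres at 0.50: 0.518 against 0.530; 8 centres at 0.15: 0.159 against 0.182). A geometric mean over centres is a different summary, not an error in itself.

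**Conclusion.** The point holds, conditionally and as a minor one. If the unseen end of the call does not average on the response scale, the visible code gives arm-specific rates far below events per person-time, with unusable intervals, whenever a centre has no events of the analysed type.

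No single factor should be quoted as the size of the error. One sixth belongs to an assumed 9 centres with 0.03 to 0.10 events per patient-year. Across 4 to 12 assumed centres the fall ranged from about 4-fold to 200-fold, partly because the stopping point of the fit sets the coefficient. Pooling small centres, if it applies here, lowers the chance of an empty centre but does not remove it.

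No confirmatory result is touched. The safety analyses are exploratory, but that status concerns multiplicity and does not justify a wrong descriptive rate.

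**What to change.** Add one sentence to section 5.5: each arm's event rate is the number of events divided by total follow-up time, with a 95% CI that allows for repeated events within a patient, and the regression model is used only for the rate ratio.

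If adjusted rates are wanted, average the predictions on the response scale over the patients' own centres. In the code this means regridding to the response together with proportional weights, with the offset set to a stated unit of follow-up. Weights without regridding are not enough.

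Correct the response and offset in the same lines at the same time. The cost is a few words before the final analysis. The downside is that crude rates are not adjusted for centre; the rate ratio remains adjusted.

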#### 5.6 Statistical software

All analyses will be performed in the current version of R or SAS (SAS Institute Inc., Cary, NC, USA). Employed R packages and the specific version are documented within the statistical report.

# 6 Appendix

#### Protocol Deviation Handling Plan, v1.0, 14 Sep 2025

Protocol deviations (PDs) are defined as any departure from the approved NOPARK protocol, GCP, or applicable regulations. Deviations are classified as **Major** or **Minor** depending on their potential impact on participant safety, trial integrity, or interpretability of efficacy/safety endpoints.

#### **Major Protocol Deviations**

- 1. Enrolment of a participant not meeting inclusion/exclusion criteria (e.g., PD diagnosis >2 years, H&Y ≥3, no DAT confirmation, use of high-dose vitamin B3).
- 2. Informed consent not obtained prior to study procedures.
- 3. Incorrect randomization or failure to randomize per protocol.
- 4. Non-adherence to investigational product (IP) administration with < 90% compliance or not taking study medication for > 14 days consecutively, or not taking study medication within 3 days from the last visit.
- 5. Non-adherence to the standardized dopaminergic regimen (Regimens A–C, see study protocol) after baseline.
- 6. Missing primary efficacy endpoint assessment (MDS-UPDRS Total) at any visit.

#### **Minor Protocol Deviations**

- 1. Missed non-primary efficacy assessments (e.g., MoCA, NMSS, EQ-5D-5L).
- 2. Missed safety laboratory samples at any visit (baseline, Week 13, 26, 39, 52).
- 3. Missed research biobank samples.
- 4. Incomplete eCRF entry not affecting data integrity.
- 5. Missing DaTscan at Week 52 when baseline DatTscan is done.

#### **Handling and Analysis**

- All deviations will be evaluated by the Sponsor (HUS).
- Each deviation will be reviewed for impact on patient safety, study integrity, and evaluability.
- The frequency and type of deviations (major/minor) will be summarized by treatment arm (the denominator for percentages will be the Full Analysis Set (FAS)).
- No formal statistical testing will be performed.
- Patients with major deviations may be excluded from the Per Protocol Set (PPS), but will remain in the FAS.

Confidential Page 20 of 21

Category	Protocol Deviation	Rationale / Potential Impact	Include in FAS	Include in PPS
Major	Enrolment of participant not meeting inclusion/exclusion criteria	Threatens study validity and endpoint interpretability	Yes	No
Major	Informed consent not obtained prior to study procedures	Regulatory and ethical violation; invalidates data	Yes	Yes
Major	Incorrect randomization or failure to randomize per protocol	Compromises trial integrity and treatment balance	No	No
Major	Non-adherence to investigational product (IP): <90% compliance	Affects treatment exposure and efficacy/safety interpretability	Yes	No
Major	Non-adherence to standardized dopaminergic regimen (Regimens A–C) post-baseline	Confounds efficacy outcomes	Yes	No
Major	Missing primary efficacy endpoint (MDS-UPDRS Total at any visit)	Primary endpoint not assessable	Yes	No

Confidential Page 21 of 21
